2.3. Study Day and Relative Day

Study Day 1 or Day 1 refers to the start of the first study drug administration. All efficacy and safety assessments at all visits will be assigned a day relative to this date.

Study day or relative day for a visit is defined as:

- Visit date - (date of Study Day 1) +1, if visit date is \geq date of Day 1
- Visit date - Date of Day 1, if visit date $<$ date of Day 1

There is no 'Day 0'.

2.4. Baseline

Baseline is defined as the last observation prior to the start of the first study drug administration.

2.5. General Analysis Rules

- Continuous data will be summarized by descriptive statistics, including number of subjects (N), mean, standard deviation (SD), median, and range (minimum; maximum).
- The minimum and maximum will be presented to the same number of decimal places as the original data. The mean and median will be rounded to one additional decimal place than the original data, while SD will be approximated to two additional decimal places.
- If a count is 0, the percentage (0%) should not be displayed. The 0 count will be displayed, but the corresponding percentage should be omitted.
- The percentages (%) in tables will be presented to 1 decimal place. If the percentage is 100% then we display it as 100% and not 100.0%.
- For continuous parameters, descriptive statistics will be presented when $n \geq 2$
- All safety analysis will be provided for each indication (AS and PsA indications) and overall population separately.

2.6. Handling Missing Data

For subjects who discontinue treatment but continue to be followed up and for whom some endpoint component data are missing, the last observation carried forward will be followed to Week 14 or Week 24 as applicable.

For a composite endpoint, if all its components are missing, no imputation will be done; if not all its components are missing, LOCF will be used to impute the missing components.

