**Handling of missing data:**

For subjects who discontinue treatment but continue to be followed up and for whom some end-point component data are missing, the last observation carried forward will be followed to Week 14 or Week 24 as applicable.

No other imputation is planned for missing data assessments.

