1.1.2 Secondary Objective

- To assess the efficacy of SC golimumab in patients with active AS or PsA as measured by reduction in signs and symptoms of arthritis in active AS or PsA at Week 14.
- To assess achievement of sustained arthritis response in patients with active AS or PsA at Week 24.

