4.1.2. Analysis Methods

Intent-to-treat population will be used for efficacy endpoints. Analysis for efficacy endpoints will be repeated on the efficacy analysis set.

The ASAS20 and ACR20 response evaluations will be performed on week 0, week 4, week 14 and week 24. The scores obtained from the respective domains will decide the responder for

ASAS20 or ACR20 criteria. Proportion of patients who achieve ASAS20 or ACR20 criteria at week 24 will be calculated, along with a 95% confidence interval.

For ASAS20, if data for percent improvement from baseline is missing at a particular assessment visit, then the response for the subject at that visit will be considered as missing.

If a subject's baseline value is zero (i.e. for ACR no disease activity for one assessment,) or missing, the subject should be considered as non-responder.

If all its components for a composite endpoint (i.e. score for subdomain as captured in CRF) are missing, the response for the endpoint at the particular visit will be set as missing; if not all its components are missing, LOCF will be used to impute the missing components and the value of the composite endpoint will be derived based on the imputed components.

If subject discontinues due to lack of efficacy, subject should be considered as non-responder.

If there is an Increase in the dose of MTX subject should be considered as non-responder.

The analysis will be done separately for each indication.

The scores for individual domains for both the ASAS20 and ACR20 will be descriptively summarized at all analysis visits.

The individual domain scores will be listed for each criteria.

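### Component-level LOCF can make a patient who stopped golimumab for a reason other than lack of efficacy a Week 14 or Week 24 responder mainly on values recorded before stopping

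*SAP*

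**What the plan says.** **Whom LOCF covers.** SAP 2.6 describes the group as "For subjects who discontinue treatment but continue to be followed up and for whom some endpoint component data are missing"; protocol section 11 (Handling of missing data) has the same rule. For them, "the last observation carried forward will be followed to Week 14 or Week 24 as applicable".

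**At what level it works.** It fills components, not responder status. SAP 4.1.2 says that after filling, "the value of the composite endpoint will be derived based on the imputed components". There is a floor. In SAP 2.6, "if all its components are missing, no imputation will be done", and in SAP 4.1.2, for the same case, "the response for the endpoint at the particular visit will be set as missing".

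**What forces non-response.** SAP 4.1.2 has one rule tied to stopping: "If subject discontinues due to lack of efficacy, subject should be considered as non-responder". Two others do not depend on stopping: an increase in MTX dose, and a zero or missing baseline value.

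**Other reasons for stopping.** SAP 3.2 also lists adverse event, non-compliance, disallowed concomitant treatment, pregnancy, disease relapse and progressive disease. None has a scoring rule. Protocol 10.2 makes several events, such as serious infection, prohibited medication and missed doses, grounds for stopping treatment, and says that stopping does not automatically withdraw the patient from the study.

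**What the result serves.** One secondary objective is "To assess achievement of sustained arthritis response in patients with active AS or PsA at Week 24". Its only endpoints are ASAS20 and ACR20 at the Week 24 visit.

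**The concern.** The plan treats one reason for stopping as failure and leaves the rest to whatever mixture of observed and carried components results. A patient can respond at Week 4, stop for an infection, return near Week 24 with only part of the assessment recorded, and be counted as a Week 24 responder on values that mostly predate stopping. A patient whose recorded reason is relapse falls under the same rule.

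Values from before stopping say little about whether response lasted to Week 24, which is what the objective asks. With a single arm, each reported proportion is read on its own, so how such patients are scored enters it directly.

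**Working it through.** **Plan's own figure.** The only planned number is the sample size, 50 AS + 50 PsA = 100. It is set by the regulator's requirement (SAP 1.4). No power, expected response, dropout or partial-missing rate is given, so the plan contains no efficacy figure to reproduce. The check is of the rule itself.

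**ASAS20 under component LOCF** (definition in SAP 4.1.1: at least 3 of 4 domains improved by >20% and >1 unit, the remaining domain not worsened by >20% and >1 unit). Suppose every carried domain meets the improvement threshold.
- 0 of 4 domains observed: response missing, nothing carried.
- 1 of 4 observed, 3 carried: responder even if the observed domain has not improved, unless it has worsened beyond the threshold.
- 2 or 3 observed: responder with at most 1 observed domain not improved and none worsened.

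**ACR20 under component LOCF** (two joint counts, both required, plus 3 of 5 other items; ESR and CRP together are one item).
- 0 of 7 items observed: response missing, nothing carried.
- 1 of 7 observed, 6 carried: responder even if the observed item, for example the acute-phase reactant, has not improved, provided it is not a joint count.
- 2 or more observed: responder with up to 2 of the five non-joint items not improved.

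So a stopped patient can be a Week 14 or Week 24 responder mostly on carried values, but only if at least one component was recorded at that visit.

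**Patients LOCF does not reach.**
- Nothing recorded at the visit: response missing.
- No completed Week 24 visit: outside the ITT set (SAP 2.2), which is the main efficacy set. Such a patient may be in the efficacy analysis set, but still with a missing Week 24 response.
- All components recorded: scored on observed data. This includes a stopping evaluation on Days 134 to 203, which SAP Table 2 assigns to Week 24.

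**Size.** One patient in a cohort of 50 is 1/50 = 2 percentage points. Let s be the number stopped for reasons with no non-response rule, f the fraction of them with a partial record at the visit, and r the fraction of those who score as responders. Compared with scoring them all as non-responders,

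points added by LOCF = 100 × s × f × r / 50.

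None of s, f or r is in the documents. Assume r = 0.6 and s = 5 or 10:
- f = 1: 100 × 5 × 0.6 / 50 = 6 points; 100 × 10 × 0.6 / 50 = 12 points.
- f = 0.5: 3 and 6 points.
- f = 0: 0 points.

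At r = 1 and f = 1 the arithmetic limit is 2 points per stopper, or 10 and 20.

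**LOCF and exclusion compared.** Assume 60% response among patients who stay on drug. Brackets give exact (Clopper-Pearson) 95% intervals.

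| Stopped of 50 | All stopped scored non-responder | All stopped left missing | All stopped partly recorded, 60% carried as responders |
|---|---|---|---|
| 5 | 27/50 = 54.0% (39.3 to 68.2) | 27/45 = 60.0% (44.3 to 74.3) | (27 + 3)/50 = 60.0% |
| 10 | 24/50 = 48.0% (33.7 to 62.6) | 24/40 = 60.0% (43.3 to 75.1) | (24 + 6)/50 = 60.0% |

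Dropping the stopped patients gives the same gap of 6 or 12 points as carrying 60% of them. A gap of that size is therefore not evidence of an LOCF effect.

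**The case against.** The strongest reply is that the rule is narrow. A reader who stops at the carry-forward clause might infer that a Week 4 response is carried whole to Week 24 for anyone who stopped, and that this inflates each cohort by 6 to 12 points. The documents do not support that. LOCF fills components, a wholly missing visit stays missing, and patients without a completed Week 24 visit leave the ITT set. The 6 to 12 points would need every stopped patient to have a partial record. This part of the reply stands in full; the true contribution could be close to zero.

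Nor is lack of efficacy the only route to forced non-response, since an MTX increase and a zero or missing baseline also lead there.

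Second, the protocol keeps stopped patients in follow-up. Scoring every one as a failure would override fully observed Week 24 responses, which is a different estimand and not a correction. This stands, and it limits the remedy to responses that the observed data do not settle.

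Third, LOCF also carries components that had not improved, so its error against the patient's actual state need not be upward. This stands too. The shift is one-way only in comparison with scoring such patients as non-responders.

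The reply does not remove the gap itself: no rule says how a partly recorded visit is scored after stopping for an adverse event, non-compliance, a disallowed drug or relapse. The surrounding text adds ambiguity. Protocol 10.1 says the last completed assessment of patients who stop for any reason will be considered, which is broader than component LOCF. SAP 4.1.2 also makes ASAS20 missing when percent improvement is missing, which sits poorly with imputing components.

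**Conclusion.** The concern holds as a limited point. Under SAP 2.6 and 4.1.2, a patient who stopped golimumab for a reason other than lack of efficacy can be a Week 14 or Week 24 responder mainly on carried on-drug components, provided at least one component is recorded at the visit and no other non-response rule applies. At Week 24 that patient counts towards the sustained-response objective.

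The size is unknown: 2 points per affected patient in a cohort of 50. Six to 12 points is an upper illustration that assumes 5 to 10 stopped patients, a partial record for all of them and 60% scored as responders; it is not an estimate of the LOCF effect. Loss of stopped patients through missing responses and the ITT definition is a separate route and could matter as much or more.

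The primary objective is safety and no hypothesis is tested, so the consequence is confined to descriptive secondary efficacy proportions. It should be corrected, but it does not threaten the main purpose of the study.

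**What to change.** 1. In SAP 2.6 and 4.1.2, state that a patient who stopped golimumab before the visit, or whose response is missing, is a non-responder when the response cannot be determined from components observed at that visit. For example, both joint counts and three other items observed as improved settle an ACR20 response even if two items are missing; one observed ASAS domain does not settle ASAS20. The existing forced non-response rules stay.
2. Report this on all treated patients in each indication, because the ITT set cannot include stopped patients without a Week 24 visit. The protocol synopsis already describes the ITT population as all enrolled patients with at least one dose, without the Week 24 condition.
3. Keep the planned component-LOCF result as a sensitivity analysis. Add a second that counts every discontinuation before the visit as non-response.
4. Reconcile protocol 10.1 with protocol section 11 and SAP 2.6 and 4.1.2, and reconcile the ASAS20 percent-improvement sentence with component LOCF. State whether an evaluation done at early stopping counts as a completed Week 24 visit.

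The cost is SAP wording, one or two extra tables, a clarification of the protocol text, and probably a slightly lower reported response rate. No visit or data collection changes.

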3. SUBJECT INFORMATION

The number of subjects in Safety analysis set will be summarized by disease indication group and overall population, separately.

The number of subjects in Safety analysis set will be listed by disease indication group.

3.1. Demographics and Baseline Characteristics

Table 3 presents a list of the demographic variables that will be summarized separately for each indication and overall population, for the Safety analysis set.

Descriptive statistics (mean, SD, median, minimum and maximum) will be presented for continuous data. Frequency and percentage will be presented for all categorical data. Subject-wise data listing will be provided.

Table 3: Demographic Variables

Continuous Variables:	Summary Type
Age (years)	Descriptive statistics (N, mean, standard deviation [SD], median and range [minimum and maximum]).
Weight (kg)	
Height (cm)	
Body Mass Index (BMI) (kg/m ²)	
Categorical Variables	
Sex (male, female)	Frequency distribution with the number and percentage of subjects in each category.
Race (Indian, Non-Indian)	

Baseline Disease Characteristics:

The table 4 presents the list of disease characteristics that will be summarized for Ankylosing Spondylitis (AS).

Table 4: Disease Characteristics Variables (For AS)

Continuous Variables:	Summary Type
Patient Global Assessment (PGA) Score	Descriptive statistics (N, mean, standard deviation [SD], median and range [minimum and maximum]).
Total and Night Spinal Pain Score	
Bath Ankylosing Spondylitis Functional Index (BASFI) Score	
Bath Ankylosing Spondylitis Disease Activity Index (BASDAI) score	
HLA B-27 Result	Counts and Percentage will be presented.
Chest X-Ray Interpretation (categories like Normal, Abnormal, Not Evaluable, Latent TB, Active TB will be presented).	

Table 5 presents the list of disease characteristics that will be summarized for Psoriasis Arthritis (PsA).

Table 5: Disease Characteristics Variables (For PsA)

Continuous Variables:	Summary Type
Tender joint count	
Swollen joint count	
Patient's Assessment of pain	Descriptive statistics (N, mean, standard deviation [SD], median and range [minimum and maximum]).
Patient's Global Assessment of Disease Activity	
Physician's Global Assessment of Disease Activity	
Health Assessment Questionnaire (HAQ)	
Erythrocyte Sedimentation Rate (ESR)	
C-reactive Protein (CRP)	

Listings will be provided for disease characteristic.

3.2. Disposition Information

Disposition will be summarized for each indication and overall population, separately.

If the patient has completed the EOS assessments (in person or telephonically) then the disposition event of that patient will be considered as “Completed”.

The summary for the treatment disposition will be as follows:

- Number of subjects enrolled
- Number of subjects discontinued the study drug

The Summary for the study disposition will be as follows:

- Number of subjects enrolled
- Number of subjects receiving study drug
- Number of subjects completed the study
- Number of subjects terminated study participation prematurely

The following primary reason for discontinuation will be summarized throughout the study under the following categories:

- Adverse Event
- Death
- Disease Relapse
- Lack of Efficacy
- Lost to Follow-Up
- Non-Compliance with Study Drug
- Received a Disallowed Concomitant Treatment
- Physician Decision
- Protocol Violation
- Study Terminated by Sponsor
- Withdrawal by Subject
- Screen Failure (Failure to Meet Eligibility Criterion)
- Pregnancy
- Progressive Disease
- Other

A listing of subjects will be provided along with the dates, study days and reason for discontinuation/ termination for the following categories:

- Subjects who discontinued study agent
- Subjects who terminated study prematurely

The summary tables and listings will be provided separately for each indication and overall population separately.

3.3. Protocol Deviations

In general, major protocol deviations may impact subjects' rights, safety or well-being, or the integrity and/or result of the clinical study.

Listing will be provided for major protocol deviations. Covid19-related Major deviations will be listed separately.

3.4. Prior and Concomitant Medications

Prior and Concomitant medications will be coded using the latest World Health Organization Drug Dictionary (WHO-DD). Prior medications are defined as any therapy used before the day of first dose (partial or complete) of study drug. Concomitant medications are defined as any therapy used on or after the same day as the first dose of study drug, including those that started before and continue on after the first dose of study drug. If start date and end date of medication is missing then this medication will be considered as prior and concomitant medication. If start date is after the date of first dose of study drug and end date is missing then decision of ongoing flag will be depend on the "Concomitant Medication End Relative to Reference Period".

Concomitant medications and prior medications will be listed separately.

4. EFFICACY

4.1. Efficacy Endpoint(s)

- Proportion of AS patients achieving ASAS20 criteria at Week 14.
- Proportion of PsA patients meeting the ACR20 criteria at Week 14.
- Proportion of AS patients achieving ASAS20 criteria at Week 24.
- Proportion of PsA patients meeting the ACR20 criteria at Week 24.

4.1.1. Definition of Endpoints

The ASAS Response Criteria (ASAS 20) is defined as:

- An improvement from baseline of >20% and >1 unit in at least 3 of the 4 ASAS domains on a scale of 0 to 10 units, and
- No worsening from baseline of >20% and >1 unit in the remaining ASAS domain on a scale of 0 to 10 units

The four ASAS domains are the following:

- a) **Patient Global Assessment of Disease (0 to 10 unit NRS):** Patient's assessment of how active their spondylitis was on average during the last week and last six months. The patient will be asked to mark the box with an X on a 0 to 10 unit NRS (Numerical Rating Scale) on which the left-hand box (0) represents '*not active*' and the right-hand box (10) represents '*very active*'.
- b) **Total and Night Spinal Pain (NRS):** Pain assessment represented by the average of total and nocturnal pain scores, both are assessed by two questions rated on a 0 to 10 NRS, where 0='no pain' and 10='most severe pain'. Total spine pain is assessed by '*How much pain in your spine due to spondyloarthritis do you have?*', and nocturnal spine pain by '*How much pain in your spine due to spondyloarthritis do you have at night?*'
- c) **Bath AS Functional Index (BASFI):** A composite score based on a patient self-administered survey of 10 questions using a 0 to 10 unit NRS that assesses a patient's degree of mobility and functional ability. The questionnaire consists of eight questions regarding function in AS and the two last questions reflecting the patient's ability to cope with everyday life. The patient will be asked to mark the box with an X on a 0 to 10 unit NRS for each of the 10 questions, on which the left-hand box (0) represents '*easy*' and the right-hand box (10) represents '*impossible*'. The resulting 0 to 100 score is divided by 10 to give a final 0 to 10 BASFI score. A higher BASFI score correlates to reduced functional ability.
- d) **Bath AS Disease Activity Index (BASDAI):** A composite score based on a patient self-administered survey of six questions using a 0 to 10 unit NRS that assesses the patient's five major symptoms of AS: 1) *fatigue*; 2) *spinal pain*; 3) *peripheral joint pain/swelling*; 4) *areas of localized tenderness*; 5) *morning stiffness severity upon wakening*; 6) *morning stiffness duration upon wakening*. The patient will be asked to mark the box with an X on a 0 to 10 unit NRS for each of the 6 questions. To give each of the five symptoms equal

weighting, the mean of the two scores relating to morning stiffness is taken. The resulting 0 to 50 score is divided by 5 to give a final 0 to 10 BASDAI score. A BASDAI score of 4 or greater is considered to be indicative of active AS disease.

The ACR response criteria (ACR20) is defined as

- **$\geq 20\%$ improvement in swollen joint count** – ACR swollen joint count, an assessment of 28 or more joints, which includes the shoulders, elbows, wrists, metacarpophalangeal (MCP) 1-5, proximal interphalangeal (PIP) 1-5 and the knees, bilaterally. Joints are classified as either *swollen* or *not swollen*.
- **$\geq 20\%$ improvement in tender joint count** – ACR tender joint count, an assessment of 28 or more joints, which includes the shoulders, elbows, wrists, MCPs 1-5, PIPs 1-5 and the knees, bilaterally. The joint count should be done by scoring several different aspects of tenderness, as assessed by pressure and joint manipulation on physical examination. The information on various types of tenderness should then be collapsed into a single *tender*-versus-*nontender* dichotomy.
- **$\geq 20\%$ improvement in 3 of the following 5 assessments:**
 - a) **Patient's assessment of pain** - A horizontal visual analogue scale (VAS) (usually 10 cm) assessment of the patient's current level of pain. The patient will be asked for severity of pain and he/she should be marked on the scale as per severity. The left side of VAS is of 'No Pain' and right side is of 'Most Severe Pain'.
 - b) **Patient's global assessment of disease activity** – A simple patient-reported VAS which assesses the patient's general health and the effect of their arthritis at that point in time. The VAS is scored by measuring from 0 to where the patient marks on the line.
 - c) **Physician's global assessment of disease activity** - A physician's global assessments of disease activity will be recorded on a VAS Scale.
 - d) **Patient's assessment of physical function as measured by the Health Assessment Questionnaire** - The functional status of the patient will be assessed by means of the Disability Index of the HAQ. This 20- question instrument assesses the degree of difficulty a person has in accomplishing tasks in 8 functional areas (*dressing, arising, eating, walking, hygiene, reaching, gripping, and activities of daily living*). Responses in each functional area are scored from 0, indicating '*no difficulty*', to 3, indicating '*inability to perform a task in that area*'.
 - e) **Acute-phase reactant** - (A Westergren Erythrocyte Sedimentation Rate and a C-reactive Protein level).

